9.1.2 Schedule of Assessments

The schedule of assessments is presented in [Table 9.1](#).

Table 9.1 Schedule of Study-Specific Procedures

Study Procedure	Screening (-42 days)	Visit (Day)						End of Study (EOS) Visit ²	Extension Phase ³
		1 (0)	2 (14)	3 (28)	4 (42)	5 (56)	6 (84)		
Study visit window (days)	N/A	0	± 3	± 3	± 3	± 3	± 3	± 7	± 7
Informed consent ¹	X								
Demographics	X								
Medical & surgical history	X								
Concomitant medication	X	X	X	X	X	X	X	X	X
Inclusion/Exclusion criteria	X								
Tumor biomarkers ⁴	X								
Physical examination ⁵	X	X	X	X	X	X	X	X	X
Pregnancy test ⁶	X								
Vital signs ⁷	X	X	X	X	X	X	X	X	X
ECOG performance score	X	X		X	X	X	X	X	X
12-Lead ECG	X	X		X	X	X	X	X	X
Clinical laboratory tests ⁸	X	X	X	X	X	X	X	X	X
Tumor assessments ⁹	X				X		X	X	X
Dispense study drug ¹⁰		X		X		X	X		X
Drug accountability				X	X	X	X	X	X
PK sampling ¹¹		X		X	X	X			
AE assessment ¹²		X	X	X	X	X	X	X	X
Patient compliance		X	X	X	X	X	X	X	X

Study Procedure	Screening (-42 days)	Visit (Day)						End of Study (EOS) Visit ²	Extension Phase ³
		1 (0)	2 (14)	3 (28)	4 (42)	5 (56)	6 (84)		
EORTC QLQ ¹³		X			X		X	X	X
Overall survival ¹⁴							X		

ECOG: Eastern Cooperative Oncology Group; ECG: Electrocardiogram; PK: Pharmacokinetics; AE: Adverse Event; EORTC: European Organization for Research and Treatment of Cancer; QLQ: Quality of Life Questionnaire.

- ¹ Informed consent must be obtained before the patient undergoes any study-specific procedures.
- ² Patients discontinuing study will attend an EOS Visit, 4 weeks after the last administration of study drug. In the event that a patient is scheduled to start a new treatment earlier than 3 weeks after the last dose of study drug, the EOS Visit should occur before the start of the new treatment and the reason documented. Tumor assessment does not need to be performed at the EOS Visit if this was conducted at the Day 84 Visit. For patients participating in the Extension Phase, the tumor assessment does not need to be performed at the EOS Visit if it has been assessed within 8 weeks of the EOS Visit.
- ³ After the first 12-week treatment cycle, patients who are progression-free will be eligible to receive further (12-week) treatment cycles with antroquinol (Extension Phase), until documented evidence of disease progression, unacceptable toxicity, non-compliance or withdrawal of consent by the patient, or the investigator decides to discontinue treatment, whichever comes first. Investigators should wait at least 7 days after the administration of study drug before initiating alternative treatment is administered. Patients discontinuing the study will attend an EOS Visit 4 weeks after last administration of study drug. Patients will attend visits every 4 weeks (\pm 7 days) during the second, third, and fourth treatment cycles in the Extension Phase. After completion of the fourth treatment cycle, patients will attend visits every 12 weeks (\pm 7 days).
- ⁴ Tumor tissue blocks or slides will be obtained from archival material or from fresh biopsy during the Screening period to determine the tumor KRAS mutation status before the patient is enrolled. A patient may be enrolled based on KRAS test results from the local laboratory. Pleural fluid cytology may be used to determine KRAS mutation status if the cytology was pathologically reviewed and reported to contain malignant cells consistent with NSCLC. Tumor tissue will also be used to study arrays of genomic and proteomic markers of interest.
- ⁵ Weight, height and body mass index (BMI) will be measured at Screening Visit only.
- ⁶ A urine pregnancy test will be performed during the Screening Visit for women of child-bearing potential. This test can be repeated during the study if required by local regulations.
- ⁷ Vital signs (respiratory rate, heart rate, blood pressure, and body temperature) will be performed at each visit. They will be obtained in the sitting position after the patient has rested for 5 minutes. The date and time of the assessment should be recorded.
- ⁸ Hematology, chemistry, and urinalysis. All tests performed at the Central Laboratory Facility.
- ⁹ Radiological and clinical tumor assessments will be performed at Screening, Day 42 and Day 84 using the RECIST criteria version 1.1. Evaluation during Screening must be performed within 14 (\pm 7) days of the date of first administration of study drug. Tumor assessments will be performed every 12 weeks during the Extension Phase.
- ¹⁰ All Screening procedures and laboratory results must be available and reviewed before the patient receives the first dose of study drug. Study drug should be taken at 8-hour intervals. The time of study drug administration should be recorded in the patient diary.
- ¹¹ Intensive PK sampling will be performed on Days 0 and 28 in all patients enrolled in Stage 1. Samples will be taken 30 minutes prior to and 0.5, 1, 2, 3, 4, 6, and 8 hours after the first dose on Day 0, and immediately before and 0.5, 1, 2, 3, 4, 6, and 8 hours after the first dose on Day 28. Sparse PK sampling will be performed on Days 28, 42, and 56 in all patients enrolled in Stage 2. At least two samples will be collected on each occasion, one of which will be a trough concentration (30 minutes prior to

dosing and approximately 8 hours after the last dose on the prior day). At least one sample per patient will be timed to coincide with the peak concentration (approximately 3 hours after dosing). The remainder may be taken at any time during the dosing interval.

- ¹² Patients must be followed for AEs from the date of informed consent until resolution or stabilization, alternative treatment for NSCLC is started, 6 months after last dose of study drug, or loss to follow-up, whichever occurs first. In the event of serious or study drug-related toxicities, the patient will be followed until resolution or stabilization. Safety follow-up data may be collected by telephone contact every 3 months after the EOS Visit.
- ¹³ Day 0 evaluation to be performed before the patient receives the first dose of study drug.
- ¹⁴ All patients who withdraw from the study drug, but consent to be followed up for survival status, will be followed up by telephone contact every 3 months, for a maximum of 6 months from the date of last administration of study drug or death, whichever occurs first..

The schedule of blood samples that will be drawn for each patient is presented in [Table 9.2](#).

Table 9.2 Schedule of Blood Sampling

Day	Sample No.	Time Schedule (hour)	Time* (hhmm)	Time Window	Activity
Stage 1					
0	N/A	-1	0700		Patient registration
0	N/A	-0.5	0730		Take blood for laboratory test
0	1	-0.5	0730		Take pre-dose sample
0	N/A	-0.25	0745		Take meal or light snack
0	N/A	0	0800		Take dose
0	2	0.5	0830	± 5 min	
0	3	1	0900	± 10 min	
0	4	2	1000	± 15 min	
0	5	3	1100	± 20 min	
0	6	4	1200	± 20 min	
0	7	6	1400	± 20 min	
0	8	8	1600	± 20 min	
28	N/A	-1	0700		Patient registration
28	N/A	-0.5	0730		Take blood for laboratory test
28	9	-0.5**	0730		Take pre-dose sample
28	N/A	-0.25	0745		Take meal or light snack
28	N/A	0	0800		Take dose
28	10	0.5	0830	± 5 min	
28	11	1	0900	± 10 min	
28	12	2	1000	± 15 min	
28	13	3	1100	± 20 min	
28	14	4	1200	± 20 min	
28	15	6	1400	± 20 min	
28	16	8	1600	± 20 min	
Stage 2					
28	1	-0.5**	N/A		Trough
28	2	3	N/A	± 1 hr	Peak
42	3	-0.5**	N/A		Trough
42	4	N/A	N/A		Random***
56	5	-0.5**	N/A		Trough
56	6	N/A	N/A		Random***

* Provided for guidance in scheduling the sampling timing for the visits; the time windows must be followed.

** Sample should be taken approximately 8 hours after the prior dose.

*** Sample may be taken at any time during the dosing interval.

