Two 7-day toxicity studies^{22,23} were performed in both Sprague-Dawley rats and beagle dogs and the maximum tolerated doses (MTD) determined were between 100 mg/kg/day for rats and 100 mg/kg/day for dogs. Two 28-days toxicity studies were conducted to determine no observed adverse effect level (NOAEL) for Sprague-Dawley rats and beagle dogs. The rat NOAEL was 30 mg/kg/day and the high dose of 100 mg/kg/day was not severely toxic.

A NOAEL in the dog was not identified (i.e., loose feces, liquid feces, and vomiting were observed at all doses); the 30 mg/kg/day dose level was tolerated and is the highest non-severely toxic dose (HNSTD).

Toxicokinetic evaluations were performed on a 7-day dog study (100, 250, 500 mg/kg/day single dose, 500 mg/kg/day 3 days dose) and the two 28-day studies mentioned above (Rat: 10, 30, 100 mg/kg/day single and 28 days dose; Dog: 10, 30, 100 mg/kg/day single and 28 days dose). Fast absorption of antroquinonol was repeatedly seen in rats and dogs with peak time (T_{max}) ranging from 0.25 to 6 hours. A trend of dose proportionality in the rat and dog was more or less shown after 1 day of treatment. After 28 days of treatment, rat and dog studies showed inconsistent phenomena in dose proportionality view, one was greater and the other was less than linear in the dose-exposure relationship.

No genotoxicity and no reproductive toxicity (up to 80 mg/kg/day) of antroquinonol was observed via Ames test, mammalian cell gene mutation test, micronucleus test, erythrocyte micronucleus test and *in vivo* study in Sprague-Dawley rats.

As known to the sponsor, no fatal or severe/serious adverse drug reaction has been reported for the marketed product (food supplement) of *Antrodia camphorata*.

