9 INVESTIGATIONAL PLAN

9.1 Overall Study Design and Plan

9.1.1 Description

This is a single-arm, open-label, Phase II study in KRAS-positive and KRAS-negative patients with stage IV (including pleural effusion) non-squamous NSCLC who have failed two lines of anti-cancer therapy. This is defined as patients with radiologically confirmed disease progression following greater than or equal to two, but less than or equal to four, prior lines of systemic anti-cancer therapy (see [Section 9.3.1](#) for a detailed description of the eligibility criteria). A maximum of 60 evaluable patients with NSCLC will receive antroquinonol, of which 30 patients will be KRAS-positive and 30 patients KRAS-negative. An evaluable patient will have received at least one dose of antroquinonol and have a valid baseline tumor assessment (see [Section 14.2](#) for further details). Enrollment will continue until the target number of evaluable patients has been enrolled.

Written informed consent must be obtained from all patients before initiating Screening. The Screening period will be up to 42 days in duration (Days -42 to -1). Following completion of all Screening assessments and confirmation of eligibility criteria, patients will receive antroquinonol 200 mg three-times-a-day (t.i.d. at 8-hour intervals) on Day 0 for 12 weeks (one treatment cycle) or until documented evidence of disease progression, unacceptable toxicity, non-compliance or withdrawal of consent by the patient, or the investigator decides to discontinue treatment, whichever comes first. Study drug should be taken at 8-hour intervals. The time of study drug administration should be recorded in the patient diary.

After the first 12-week treatment cycle, patients who are progression-free will be eligible to receive further (12-week) treatment cycles with antroquinonol (Extension Phase), until documented evidence of disease progression, unacceptable toxicity, non-compliance or withdrawal of consent by the patient, or the investigator decides to discontinue treatment, whichever comes first. Investigators should wait at least 7 days after the last administration of study drug before initiating alternative treatment.

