9.3 Selection of Study Population

9.3.1 Inclusion Criteria

Patients eligible for enrollment in the study must meet all of the following criteria:

1. Cytologically or histologically confirmed non-squamous NSCLC Stage IV (including pleural effusion)
2. Radiologically confirmed disease progression following greater than or equal to two, but less than or equal to four, prior lines of systemic anti-cancer therapy, one of which should be a platinum-based regimen, OR the patient has refused treatment with approved treatment modalities, OR the investigator feels that the patient is not a candidate for other systemic therapy. Patients with epidermal growth factor receptor (EGFR)-positive mutations should have been offered treatment with an EGFR-TK inhibitor prior to enrolment in this study. Adjuvant therapy with or without maintenance therapy would count as one line of systemic therapy. A line of therapy requires at least two 3-4 week complete cycles unless it was stopped due to toxicity, in which case it would count as one line of therapy
3. At least one radiologically measurable target lesion per RECIST version 1.1
4. Fresh or archival biopsy tissue available to determine KRAS tumor mutation status
5. At least 18 years of age at the time of signing informed consent
6. Life expectancy of at least 3 months
7. Written informed consent that is consistent with ICH Tripartite Guideline on Good Clinical Practice (GCP) guidelines
8. Patient or legally acceptable representative has granted written informed consent before any study-specific procedures (including special Screening tests) are performed
9. Eastern Cooperative Oncology Group (ECOG) performance score of 0, 1 or 2

10. Hemoglobin ≥ 9.0 g/dL; platelets $\geq 100 \times 10^9/L$; ANC $\geq 1.5 \times 10^9/L$ without the use of hematopoietic growth factors
11. Bilirubin and creatinine less than $2 \times$ upper limit of normal (ULN) for the institution
12. Albumin ≥ 2.5 g/dL
13. Aspartate aminotransferase (AST) and alanine aminotransferase (ALT) less than $5 \times$ ULN for the institution
14. Prothrombin time less than $1.5 \times$ ULN for the institution
15. Potassium, magnesium and phosphorus within the normal range for the institution (supplementation is permissible)
16. Willing to use two medically accepted and effective methods of contraception from the list below during the study (both men and women as appropriate) and for 3 months after the last dose of study drug:

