9.3.2 Exclusion Criteria

Patients meeting any of the following criteria must not be enrolled in the study:

1. Chemo-, hormone- or immunotherapy, within 4 weeks or within less than four half-lives of the date of first administration of study drug and/or persistence of toxicities of prior anti-cancer therapies which are deemed to be clinically relevant
2. Radiotherapy within the past 2 weeks prior to the date of first administration of study drug.
3. Previous treatment with a histone deacetylase (HDAC) inhibitor or an EGFR inhibitor within at least 4 weeks of the date of first administration of study drug
4. Treatment with any drug(s) known to be a strong inhibitor or inducer of CYP2C19, CYP3A4, CYP2C8, and CYP2E1, within 14 days of the date of first administration of study drug

5. Brain metastases which are symptomatic; patients with treated brain metastases are eligible with stable brain disease for at least 4 weeks without the requirement for steroids or anti-epileptic therapy
6. Inability to swallow oral medications or a recent acute gastrointestinal disorder with diarrhea e.g., Crohn's disease, malabsorption, or Common Terminology Criteria for Adverse Events (CTCAE) Grade > 2 diarrhea of any etiology at baseline
7. Other malignancies diagnosed within the past 5 years (other than curatively treated cervical cancer *in situ*, non-melanoma skin cancer, superficial bladder tumors Ta [non-invasive tumor] and TIS [carcinoma *in situ*], or non-metastatic prostate cancer stage 1 to 2, which has been previously treated with surgery or radiation therapy, and serum prostate-specific antigen is within normal limits [test performed within the past 12 months prior to the date of first administration of study drug])
8. Patients with any serious active infection (i.e., requiring an intravenous antibiotic, antifungal, or antiviral agent)
9. Patients with known HIV, active hepatitis B or active hepatitis C
10. Patients who have any other life-threatening illness or organ system dysfunction, which in the opinion of the investigator, would either compromise patient safety or interfere with the evaluation of the safety of the study drug
11. Known or suspected substance abuse or alcohol abuse
12. Women of child-bearing potential or men who are able to father a child unwilling to use two medically accepted and effective methods of contraception during the study (as specified in the inclusion criteria)
13. Pregnancy or breast feeding

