13.10.6 Pregnancy

Patients with child-bearing potential must be confirmed as not being pregnant at Screening and willing to use effective methods of contraception during the study and for 3 months after the last dose of study drug (as defined in [Section 9.3.1](#), Inclusion Criterion 16). Following administration of study drug, pregnancy cases in any female patient will be reported if known until the patient completes or withdraws from the study. The pregnancy will be reported immediately by phone and by faxing a completed Pregnancy Report to the sponsor (or designee) within 24 hours of knowledge of the event. The pregnancy will not be processed as an SAE; however the investigator will follow the patient until completion of the pregnancy and must assess the outcome in the shortest possible time but not more than 30 days after completion of the pregnancy.

The investigator should notify the sponsor (or designee) of the pregnancy outcome by submitting a follow-up Pregnancy Report. If the outcome of the pregnancy meets the criteria for immediate classification of an SAE (e.g., spontaneous or therapeutic abortion [any congenital anomaly detected in an aborted fetus is to be documented], stillbirth, neonatal death, or congenital anomaly), the investigator will report the event by phone and by faxing a completed SAE form to the sponsor (or designee) within 24 hours of knowledge of the event.

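### The only mandatory pregnancy test is at Screening and can be up to 42 days old at first dose; require a negative test within 7 days of dosing or on Day 0

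*Protocol*

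**What the plan says.** Protocol Section 9.1.1 sets the length of Screening: "The Screening period will be up to 42 days in duration (Days -42 to -1"). Table 9.1 marks the pregnancy test in the Screening column and nowhere else. Footnote 6 explains the mark: "A urine pregnancy test will be performed during the Screening Visit for women of child-bearing potential". It adds: "This test can be repeated during the study if required by local regulations". Section 9.1.3.1 gives the same instruction, under a heading that allows Screening up to 42 days before Day 0. Section 13.10.6 agrees with this timing: "Patients with child-bearing potential must be confirmed as not being pregnant at Screening".

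The Visit 1 (Day 0) list in Section 9.1.3.2 has no pregnancy test.

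Exclusion criterion 13 (Section 9.3.2) reads: "Pregnancy or breast feeding". Inclusion criterion 16 (Section 9.3.1) requires that patients be "Willing to use two medically accepted and effective methods of contraception from the list below during the study". Section 7.3 reports: "No genotoxicity and no reproductive toxicity (up to 80 mg/kg/day) of antroquinonol was observed via Ames test", among other tests.

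**The concern.** An exclusion protects the patient only if the check behind it is recent enough to describe her condition when she is first exposed. Here the exclusion concerns a state that can change between Screening and Day 0, and the plan sets no maximum age for the result. A woman who conceives after an early Screening test could start antroquinonol with no scheduled step that would reveal the pregnancy. The stake is fetal and maternal safety. The efficacy analysis is not touched.

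**Working it through.** No sample-size or error-rate figure bears on this point. The check sets the relevant sections side by side, with one subtraction.

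**1. Longest age of the mandatory test at first dose**
- Earliest permitted Screening day: Day -42 (Section 9.1.1; heading of Section 9.1.3.1).
- First dose: Day 0 (Section 9.1.3.2).
- Maximum age: 0 - (-42) = 42 days.

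**2. Does anything between Screening and dosing refresh the result?**
- Table 9.1, pregnancy-test row: Screening only.
- Section 9.1.3.2, Day 0 list: vital signs, ECG, laboratory tests and other items, but no pregnancy test.
- Footnote 6 and Section 9.1.3.1: a repeat is permitted where local rules demand it, so the protocol itself sets no minimum.
- Section 13.10.6: confirmation is tied to Screening, with no interval to first dose.
- Section 9.1.1: "Following completion of all Screening assessments and confirmation of eligibility criteria, patients will receive antroquinonol 200 mg". The only pregnancy information scheduled for that confirmation is the Screening test. Reviewing an old result before dosing does not make it newer.

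**3. Does the protocol set tighter windows elsewhere within Screening?**
Yes. The baseline scan must fall within 14 (± 7) days of first dose (Table 9.1, footnote 9; Section 11.2.1), which gives at most 14 + 7 = 21 days. The pregnancy test has no such limit of its own.

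**4. Effect of the proposed window**
With a 7-day limit the maximum age falls from 42 to 7 days, a reduction of 42 - 7 = 35 days. With a Day 0 pre-dose test it falls to 0.

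**The case against.** The strongest case on the other side has four parts.

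*The 42 days may overstate the gap.* Footnote 6 places the test at the Screening Visit, and Section 9.1.3.1 requires the tumor evaluation at that visit to be within 14 (± 7) days of first dose. If the Screening Visit is a single occasion, the test is at most 21 days old. The reading is possible, but the heading of Section 9.1.3.1 itself allows up to 42 days and nothing says that all Screening procedures share one date. So 42 days stands as an upper limit. Even at 21 days the check would not reach the dosing date.

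*Contraception covers the interval.* Criterion 16 and exclusion 12 do lower the risk. However, the protocol requires a test in addition to contraception, so it does not treat contraception as sufficient.

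*The preclinical findings are reassuring.* Section 7.3 reports no reproductive toxicity up to 80 mg/kg/day. This also lowers the concern, yet the protocol still excludes pregnancy and asks for contraception for 3 months after the last dose.

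*Exclusion 13 is not confined to the test result.* True: a pregnancy known on Day 0 would still exclude the patient. The gap concerns one that nobody yet knows about.

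A reader might go further and infer that eligibility laboratory values generally may be out of date at dosing, or that prothrombin time is never measured. The protocol does not support either inference. Laboratory tests are redrawn on Day 0, Section 9.1.3.2 requires repeat results to be reviewed before the first dose, Section 9.1.1 requires eligibility to be confirmed, and Section 13.9 asks the investigator to judge continued eligibility. Inclusion criterion 14 cannot be met without a prothrombin time value, and the Section 13.9 list, which omits it, describes tests taken at every visit and may not be exhaustive. What remains there is drafting clarity.

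**Conclusion.** The point holds for the pregnancy test. With the plan followed exactly, the first dose can be given on a negative urine test up to 42 days old, although pregnancy is an exclusion. The figure rests on two readings of the text: that the test may be done on any Screening day, and that no local regulation requires a repeat. It bounds the interval and does not estimate how many of the at most 60 evaluable patients would be affected, which the protocol gives no means of estimating. Contraception and the preclinical results reduce the risk without closing the gap. No primary or secondary result, power or significance level changes. This is a cheap improvement in patient safety.

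**What to change.** Require a negative urine pregnancy test, for women of child-bearing potential, within 7 days before first dose or on Day 0 before dosing. The 7-day figure is a proposal; the protocol does not supply one. Make the change in four places: the Visit 1 list in Section 9.1.3.2, footnote 6 of Table 9.1, Section 13.10.6, and the Visit 1 column of Table 9.1. The 42-day Screening period can stay for consent, history and KRAS tissue. The cost is protocol wording and an occasional repeated urine test when Screening runs long.

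Two editorial notes can go in with the same amendment. List prothrombin time among the Screening tests, because criterion 14 depends on it. Align footnote 10 of Table 9.1 and Section 13.9, which name only the Screening results or do not mention repeats, with Section 9.1.3.2, which also covers repeat laboratory results.
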